6.2.7.1. Prospectively-Defined Efficacy Analyses

Detailed information for the prospectively-defined efficacy endpoints can be found in [Section 5.1.1](#). A binary response variable (Yes, No) will be analyzed to compare G1T28 and placebo using stratum-adjusted method to account for the ECOG status (0-1 vs 2) as the stratification factor. The adjusted proportion difference (trilaciclib vs placebo) and its 80% CIs will be calculated using CMH weight outlined in [Kim et al. 2013](#). The two-sided p-value will be calculated using stratified exact Cochran-Mantel-Haenszel (CMH) method. The following binary response variables will be analyzed:

- Occurrence of a febrile neutropenia AE during the treatment period (refer to [Section 5.1.1.1](#));
- Occurrence of a RBC transfusion (actual and eligible) during the treatment period (refer to [Section 5.1.1.2](#));
- Occurrence of a platelet transfusion (actual and eligible) during the treatment period (refer to [Section 5.1.1.3](#));
- Occurrence of a GCSF administration during the treatment period (refer to [Section 5.1.1.4](#));

- Occurrence of an ESA administration during the treatment period (refer to [Section 5.1.1.5](#));
- Occurrence of an IV antibiotic administration during the treatment period (refer to [Section 5.1.1.6](#));
- Occurrence of an infection SAE during the treatment period (refer to [Section 5.1.1.7](#));
- Occurrence of a pulmonary infection SAE during the treatment period (refer to [Section 5.1.1.7](#)).

Time (days) to event endpoints will be summarized using Kaplan-Meier method, and the descriptive statistics of median, 25% and 75% percentiles along with their 95% CIs will be calculated for endpoints described in [Sections 5.1.1.8, 5.1.1.9, and 5.1.1.11](#).

In addition to the summary from Kaplan-Meier method, for the endpoints of

- Overall duration (days) of Grade 4 neutropenia;
- Overall duration (days) of Grade 3/4 neutropenia;
- Time (days) to first occurrence of a MAHE event,

the two-sided p-value will be obtained from the stratified Kaplan-Meier method to account for the ECOG status (0-1 vs 2) as the stratification factor. The hazard ratio (HR) between the two treatments (trilaciclib vs placebo), together with its 80% CIs will be calculated from a Cox proportional hazard model in which treatment and baseline ECOG status (0-1 vs 2) will be included as fixed effects. For the time (days) to first occurrence of a MAHE event, a graphical display of cumulative incidence will be presented.

For the endpoints specified in [Section 5.1.1.10](#), in addition to descriptive statistics summary, appropriate graphical display will be provided to help viewing the trend of change over time. Moreover, each of the ANC change over time (i.e. observed value at windowed visit, cycle NADIR, and ANC at each scheduled Day 1 of a cycle) specified above will be done using three distinct data sets to evaluate the confounding effect of GCSF administration: all patients or cycles regardless of GCSF administration; inclusion of only those patients or cycles who had concurrent GCSF administration; and inclusion of only those patients or cycles who did NOT have concurrent GCSF administration. The “with” and “without” GCSF analyses are subsets of the total patient or cycles.

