
---

lymphocytes, etc.). Analyses comparing treatment groups for Part 2 will adjust for baseline ECOG and other relevant parameters. Event rates will be calculated based on cumulative E/P exposure to account for potential differences in E/P exposure across treatment arms.

Summaries of safety data will be performed using the safety population. Adverse event data will be coded to system organ class and preferred term using the Medical Dictionary for Regulatory Activities (MedDRA; Version 17.1 or later). The number and percentage of patients experiencing any treatment-emergent AE, overall, and by system organ class and preferred term will be tabulated. The incidence rates adjusted by cumulative exposure will also be presented overall and by cycle. Absolute values and changes from baseline in vital signs, ECG readings, and hematology and clinical chemistry parameters will be tabulated at each visit during the Treatment Phase. Toxicities for clinical labs will be characterized according to the CTCAE, Version 4.03. Shifts in toxicity grades from baseline to each visit will be summarized. Overall disease responses as determined by RECIST, Version 1.1 will be summarized by response level at each visit and best overall response.

Progression-free survival and overall survival will be summarized using Kaplan-Meier methods.

Blood samples will be collected in the Phase 1b dose-finding portion of Part 1 of the study for the determination of G1T28, etoposide, and carboplatin plasma concentrations. Plasma PK parameters will be calculated for each analyte, when possible, including  $C_{max}$ ,  $T_{max}$ ,  $AUC_{0-t}$ ,  $AUC_{0-\infty}$ ,  $t_{1/2}$ ,  $V_z$ , and CL. Pharmacokinetic results will be analyzed and reported for the PK analysis set, separately for each analyte. Plasma concentration-time data will be tabulated descriptively and graphed for each blood sampling day.

Pharmacokinetic parameters will be calculated using noncompartmental methods based on the plasma concentration-time data. Pharmacokinetic parameters will be summarized descriptively by visit and analyte. If applicable, G1T28 PK data will also be summarized by dose level.

---

Rationale for Number of Patients

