#### 13.4.2.2. Analysis of Hematologic Toxicity Endpoints

The number and percentage of patients with Grade 3 and 4 hematologic toxicities at each cycle and overall during the Treatment Phase will be tabulated for each type of hematologic toxicity and across all type of hematologic toxicities. Percentages for by-cycle summaries will be based on the number of patients treated in the cycle. For tabulations performed based on data collected in Part 2, the difference in rates between treatment groups will be calculated. Two-sided 95% CIs will be constructed around the difference in treatment groups. If there are substantial dose reductions, an incidence rate, adjusting for cumulative exposure, may be reported to account for differing amount of exposure by cycle.

The total number of Grade 3 and 4 hematologic toxicities will be summed over the entire Treatment Phase per patient, separately for each type of hematologic toxicity and across all types of hematologic toxicities. To account for differing amount of exposure, a toxicity rate will be calculated for each patient, and defined relative to cumulative exposure (total number of toxicities divided by cumulative exposure). A recurrent events model may be performed to estimate the incidence of Grade 3 or higher hematologic toxicities and test for the difference between treatment groups.

For each hematologic parameter and cycle, the following shift summaries will be performed: from predose toxicity to maximum ontreatment toxicity; from predose toxicity to end of cycle toxicity; from maximum postdose toxicity to end of cycle toxicity.

Hematologic recovery will be defined in the SAP. The number and percentage of patients with hematologic recovery will be calculated at each cycle. Time to postdose recovery within a cycle will be estimated using the Kaplan-Meier method. A Cox proportional hazard model adjusted for baseline hematologic toxicity and ECOG will also be performed.

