2.3. Number of Patients

Overall, up to 110 patients will be enrolled in the study. The sample size for this study is determined by clinical rather than statistical considerations.

In Part 1, approximately 40 patients will be enrolled, assuming up to 3 cohorts. Cohorts will consist of 6 patients each in the Phase 1b dose-finding portion of Part 1 and up to 18 patients in the Phase 2a expansion portion of Part 1 at the selected dose to be used in Part 2. Additional patients may be enrolled in the Phase 1b dose-finding portion of Part 1 if more than 1 cohort is enrolled. In Part 2, 70 patients will be randomly assigned (1:1 ratio) to 1 of 2 groups: G1T28 administered IV with E/P therapy (Group 1) or placebo administered IV with E/P therapy (Group 2). With 35 patients, the precision for point estimates in each arm is as follows: the 95% confidence interval (CI) width for binary endpoints based on Wilson score intervals are at most the observed proportion ± 0.157 . The 95% CI width for continuous endpoints using the t-distribution are the observed mean ± 0.344 *standard deviation of the endpoint.

The study will be conducted at up to 80 centers in North America and Europe.

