6.1.4. Adjustment for Covariates

The baseline ECOG status (0, 1, and 2) which was used as the stratification factor will be included as a covariate in relevant statistical modeling for data from Part 2.

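### The Part 2 comparison of RBC transfusion adjusts for ECOG only and leaves out baseline hemoglobin: a valid analysis, but less efficient than the collected data allow

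*SAP*

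**What the plan says.** SAP 6.2.7.1 covers RBC transfusion together with the other binary endpoints: "A binary response variable (Yes, No) will be analyzed to compare G1T28 and placebo using stratum-adjusted method to account for the ECOG status" (strata 0-1 vs 2). The risk difference uses CMH weights with an 80% CI, and the p-value is from a stratified exact CMH test. For Grade 4 and Grade 3/4 neutropenia duration and time to first MAHE, the hazard ratio comes from a "Cox proportional hazard model in which treatment and baseline ECOG status (0-1 vs 2) will be included as fixed effects". SAP 6.1.4 names no covariate beyond ECOG.

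The protocol is broader, but unevenly so:

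- Synopsis, Statistical Analysis: "Analyses comparing treatment groups for Part 2 will adjust for baseline ECOG and other relevant parameters". The other parameters are not named.
- Sections 13.4.2.1 and 13.4.2.2: a baseline hematologic value enters the ANCOVA and AUC models for count kinetics. For time to hematologic recovery, "A Cox proportional hazard model adjusted for baseline hematologic toxicity and ECOG will also be performed".
- Sections 13.4.2.2 and 13.4.2.4: transfusion incidence gets a difference in rates with a 95% CI, and no baseline count is mentioned.

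SAP Section 7 lists the ANCOVA and AUC models as removed. It does not list the recovery Cox model.

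On the endpoint, SAP 5.1.1.2 counts a cycle as an RBC event if the patient was transfused or had hemoglobin below 8.0 g/dL. Protocol 7.1.1 admits patients from 9.0 g/dL with no ceiling. Hemoglobin is measured at screening and on Day 1 of each cycle (Protocol Table 9-1).

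**The concern.** Part of the RBC endpoint is a threshold crossing of a variable measured at entry. A patient entering at 9.2 g/dL is 1.2 g/dL from an event; one entering at 14 g/dL is 6 g/dL away. Within an ECOG stratum the planned analysis treats the two as exchangeable. If baseline hemoglobin predicts the event, that variation stays in the standard error when a covariate could remove it.

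This matters because SAP 5.1.1 places RBC transfusion among its primary prospectively-defined endpoints, and there are only 35 patients per arm. Once the ANCOVA, AUC and recovery models are gone, no baseline count enters any between-arm comparison in a trial about preserving blood counts, and the SAP does not say what became of the synopsis's further parameters.

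**Working it through.** **Inputs.** SAP 2.3: "In Part 2, 70 patients will be randomly assigned (1:1 ratio) to 1 of 2 groups", so 35 per arm. SAP 6.1.1: two-sided 20% level with 80% CIs. No design event rates or effect sizes exist: "The sample size for this study is determined by clinical rather than statistical considerations". Every rate and prognostic strength below is therefore an assumption.

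**The plan's own figures.** SAP 2.3 gives per-arm 95% half-widths of 0.157 (binary, Wilson) and 0.344 SD (continuous).

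- Wilson, p = 0.5, n = 35: 1.96 × √(0.25/35 + 1.96²/(4 × 35²)) / (1 + 1.96²/35) = 0.1745/1.1098 = 0.157.
- t: t(0.975, 34)/√35 = 0.3435.

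Both reproduce. They are single-arm figures and do not address the between-arm comparison.

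**Between-arm baseline, assumed 40% vs 20%.** SE = √(0.24/35 + 0.16/35) = 0.1069. The 80% half-width is 1.2816 × 0.1069 = 0.137. Power = Φ(0.20/0.1069 − 1.2816) = Φ(0.589) = 0.72.

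**Analytic effect of adjustment.** If the covariate explains a share R² of outcome variance, the SE is multiplied by √(1 − R²) and the equivalent sample size is 35/(1 − R²) per arm.

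| R² | 80% half-width | Power | Equivalent n per arm |
|---|---|---|---|
| 0 | 0.137 | 0.72 | 35.0 |
| 5% | 0.134 | 0.74 | 36.8 |
| 10% | 0.130 | 0.76 | 38.9 |
| 20% | 0.123 | 0.79 | 43.8 |
| 30% | 0.115 | 0.83 | 50.0 |

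**Simulation against the planned estimator.** The comparator is the ECOG CMH-weighted difference; the alternative is a standardized risk difference from a logistic model with treatment, ECOG and baseline hemoglobin. Assumptions: 35 per arm, 15% of patients at ECOG 2, ECOG not prognostic, RBC rates 35-40% vs 15-20%, and bivariate-normal baseline and on-treatment hemoglobin.

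| Latent correlation | Variance ratio, adjusted/planned | Power gain at two-sided 20% |
|---|---|---|
| 0.3 | about 0.97 | about 0 |
| 0.5 | 0.86-0.89 | 3-4 points |
| 0.7 | 0.71-0.76 | about 9 points |

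Under a null of 25% in both arms, both methods reject in 21-23% of trials, so the gain is not bought with inflated size. A separate simulation against a plain difference (40% vs 20%) gives variance ratios of 1.01, 0.98, 0.87 and 0.76 for odds ratios per SD of 1.0, 1.65, 2.7 and 4.5. A weak covariate gains almost nothing and costs almost nothing.

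**Neutropenia duration.** Cox models were simulated with 70 patients, no censoring, and a true conditional log HR of 0.5. With a baseline covariate of log HR 0, 0.3, 0.5 or 0.8 per SD, power without and with it is 0.79 to 0.78, 0.73 to 0.77, 0.69 to 0.76 and 0.57 to 0.78. The SE of the log HR does not fall (0.25 without, 0.26 with). The gain arises because the unadjusted log HR shrinks toward zero (averages 0.51, 0.47, 0.44 and 0.36) while the adjusted one stays near 0.51.

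**Events available.** 35 × (0.35 + 0.15) = 17.5 and 35 × (0.40 + 0.20) = 21, so roughly 18-21 RBC events across both arms.

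**The case against.** The strongest reply is that nothing here is invalid. Stratifying by the randomization factor gives a sound comparison whose interval already allows for chance imbalance in hemoglobin. The sample size is not power-based, the primary objectives are dose and safety, and Protocol 13.2.3 describes the study as descriptive. With 18-21 events, preferring a logistic model to an exact test is debatable. The endpoint also includes transfusion for symptomatic anemia at the investigator's discretion (Protocol 8.7), which weakens its link to baseline hemoglobin. All of this stands. It limits the point to efficiency and is why CMH should be kept.

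It also rules out several stronger readings:

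- A reader might infer that the protocol promised baseline hemoglobin, platelets and ANC for these comparisons. It did not. The synopsis names no parameter, and the transfusion method names no covariate. The recovery Cox model concerns another endpoint and uses baseline toxicity; entry requires ANC of at least 1.5 × 10⁹/L, so screening neutropenia is Grade 0 or 1 at most.
- A reader might infer wider intervals for neutropenia duration. The calculation shows no reduction in the SE, only possible power. Adding ANC also makes the hazard ratio conditional on ANC.
- A reader might extend the case to platelet transfusion. Entry is at 100 × 10⁹/L or more and the event threshold is 10 × 10⁹/L or less, so little gain is to be expected there.
- A reader might take the three-level wording in SAP 6.1.4 ("The baseline ECOG status (0, 1, and 2) which was used as the stratification factor will be included as a covariate in relevant statistical modeling") as a wrong stratified analysis. It is a drafting slip: SAP 2.2 and 6.2.7.1 use 0-1 vs 2.

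**Conclusion.** The point holds for RBC transfusion, as a loss of efficiency and not of validity. Under assumed rates of 35-40% vs 15-20% with 35 per arm, adding baseline hemoglobin reduces the variance of the risk difference by about 3%, 11-14% or 24-29% at latent correlations of 0.3, 0.5 and 0.7. Power at the two-sided 20% level rises by about 0, 3-4 or 9 points.

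The documents give neither the correlation nor the event rates, so where the trial falls in this range is unknown, and at the low end there is nothing to gain. The comparison is with the CMH-weighted difference and its interval, not with the exact CMH p-value, and it assumes that ECOG is not prognostic.

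For neutropenia duration the case is weaker: possible power, and no narrower interval. For platelet transfusion there is no case for change. The undeclared departure from the protocol comes down to one unlisted recovery Cox model and an unspecific synopsis commitment that the SAP neither carries out nor withdraws.

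**What to change.** Before unblinding:

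1. In SAP 6.2.7.1, pre-specify for RBC transfusion a standardized risk difference with an 80% CI from a logistic model with treatment, ECOG (0-1 vs 2) and baseline hemoglobin, using the study baseline already defined in SAP Section 5. Report it alongside the stratified exact CMH result.
2. For Grade 4 and Grade 3/4 neutropenia duration, add a supportive Cox model with treatment, ECOG and baseline ANC, and state that its hazard ratio is conditional on ANC.
3. Keep CMH alone for platelet transfusion.
4. In SAP 6.1.4, correct the ECOG categories to 0-1 vs 2.
5. In SAP Section 7, list the dropped recovery Cox model. Items 1 and 2 would then say which further parameters the synopsis sentence covers.

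The cost is SAP wording and a little more programming; no new data are needed. The downside is a model-based interval resting on roughly 18-21 events, which is why the CMH analysis stays beside it.

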##### 13.4.2.1. **Analysis of Hematologic Parameter Kinetic Endpoints**

Hematologic parameter values will be tabulated with descriptive statistics using absolute counts, change, and percent change values. By-visit tabulations will include values at study

baseline (ie, prior to first dose of study treatment) and each postbaseline visit through all cycles and the Post-Treatment Visit. Changes and percent changes will be calculated at each postbaseline value. Additional tabulations for each cycle of treatment will include predose, nadir, maximum postnadir, and end of cycle values. The change and percent changes from predose to nadir, predose to end of cycle, nadir to maximum postnadir, and nadir to end of cycle values will also be tabulated for each cycle of treatment. Analysis of covariance (ANCOVA) models will be performed for summaries on Part 2, separately at each visit and for each of the following parameters as dependent variables: change from baseline and percent change from baseline. Analysis of covariance models will be performed separately at each cycle and for each of the following parameters as dependent variables: predose (for cycles 2 and onward), nadir, the Post-Treatment Visit counts, change from predose to nadir, predose to end of cycle, nadir to maximum postnadir, and nadir to end of cycle; and percent change from predose to nadir, predose to end of cycle, nadir to maximum postnadir, and nadir to end of cycle. The models will include terms for treatment, ECOG at entry (0 and 1 or 2), and baseline hematologic parameter value. The least square (LS) mean for each treatment group and LS mean difference between treatment groups will be reported. The treatment by ECOG interaction and treatment by baseline hematologic value will be tested. If a significant treatment by ECOG interaction exists, the LS means and LS mean differences will be reported at each level of ECOG at entry. If a treatment by baseline hematologic parameter interaction exists, the LS means and LS mean differences will also be reported at various levels of the covariate (10%, 25%, 50%, 75%, 90%). Two-sided 95% CIs will be constructed around the LS mean differences in treatment groups.

The most extreme Treatment Phase nadir value and the cycle at which the most extreme nadir occurred will be summarized descriptively. Time to nadir will be summarized descriptively for each cycle and is calculated for each cycle and defined as date of nadir minus predose date + 1.

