4. PROSPECTIVELY DEFINED ANALYSES

As outlined in the protocol, trilaciclib is an IV cyclin dependent kinase (CDK) 4/6 inhibitor being evaluated for its ability to decrease chemotherapy-induced myelosuppression when administered in combination with cytotoxic chemotherapy. Unlike granulocyte-colony stimulating factor (GCSF), which stimulates production of neutrophils, and transfusions, which only replace red blood cell (RBC) or platelets, trilaciclib is hypothesized to facilitate myelopreservation of all hematopoietic lineages including neutrophils, RBC, platelets, lymphocytes, etc.

Based on the mechanism of action, it is also hypothesized that the effects of trilaciclib-induced myelopreservation may be more obvious after patients receive repeated rounds of chemotherapy. For example, SCLC patients treated with carboplatin and etoposide often have more dosing delays and hematologic-related adverse events (AEs) after multiple cycles due to repeated damage to the bone marrow. In contrast, addition of trilaciclib to carboplatin and etoposide is theorized to counteract the chemotherapy-induced damage and allow patients to receive multiple cycles of therapy with less dose delays and fewer hematologic-related AEs.

To capture these two aspects of trilaciclib benefit, the following analyses are prospectively proposed in [Table 3](#) and their associated endpoint derivation and analysis methods will be detailed in [Sections 5.1.1 and 6.2.7.1](#).

Table 3 Prospectively Defined Analyses

Proportion of patients with febrile neutropenia during the treatment period
Duration of Grade 4 neutropenia
Duration of Grade 3/4 neutropenia
Average ANC over time (for all cycles; with and without GCSF subset analysis)
Average ANC NADIR over time (for all cycles; with and without GCSF subset analysis)
Average ANC at each scheduled Day 1 of a cycle (for all cycles; with and without GCSF subset analysis)
Average hemoglobin over time (for all cycles)
Average platelet count over time (for all cycles)
Average lymphocyte count over time (for all cycles)
Proportion of patients with RBC transfusions (includes actual or eligible) during the treatment period
Proportion of patients with platelet transfusions (includes actual or eligible) during the treatment period
Proportion of patients with GCSF use during the treatment period
Proportion of patients with ESA use during the treatment period
Proportion of patients with IV antibiotic use during the treatment period

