7. CHANGE FROM THE PROTOCOL

The endpoints and analyses listed below are based on the Statistics Section in the Protocol Amendment 7, dated 11 May 2016. The list displays the endpoints and analyses which are removed from the initial analysis and are therefore not described in the SAP..

Protocol Section 13.3.1 (Efficacy Endpoints):

- Hematologic kinetic endpoints:
 - Change and percent change in hematologic parameter values from predose for a particular cycle to the end of that cycle
 - Change and percent change in hematologic parameter values from predose for a particular cycle to nadir for that cycle
 - Rate of change in hematologic parameter values from predose for a particular cycle to nadir for that cycle
 - Change and percent change in hematologic parameter values from nadir for a particular cycle to the end of that cycle
 - Rate of change in hematologic parameter values from nadir for a particular cycle to the end of that cycle
 - Area under the curve in hematologic parameter values from predose for a particular cycle to the end of that cycle
 - Area under the curve in hematologic parameters from predose for a particular cycle to nadir for that cycle
 - Area under the curve in hematologic parameter values from nadir for a particular cycle to the end of that cycle
 - Time to hematologic parameter value nadir by cycle
 - Time to return to predose hematologic parameter values by cycle
 - Proportion of patients with a return to predose hematologic parameter values by cycle
- Exploratory efficacy endpoints:
 - Composite hematologic score

Protocol Section 13.3.2.1 (Analysis of Hematologic Parameter Kinetic Endpoints)

- Additional tabulations for each cycle of treatment in maximum postnadir values.
- The tabulation of the changes and percent changes from predose to nadir, predose to end of cycle, nadir to maximum postnadir, and nadir to end of cycle values for each cycle of treatment.
- Analysis of covariance (ANOVA) models on hematologic parameter kinetic endpoints
- Summarization of time to nadir.
- Descriptive statistics and ANOVA of AUC in hematologic parameters

- Repeated-measures model of AUC
- Summary of proportion of patients return to predose value for each cycle. calculation on incidence rate, adjusting for cumulative exposure
- Analysis of time to return to predose level for each cycle using Kaplan-Meier method.
- Analysis of Time to return to postnadir predose levels

Protocol Section 13.3.2.2 (Analysis of Hematologic Toxicity Endpoints)

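### Six of the 17 prospectively defined analyses (the ANC, hemoglobin, platelet and lymphocyte averages) have no Part 2 treatment estimate specified, because the SAP removes the protocol's baseline-adjusted ANCOVA and names no replacement

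*SAP*

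**What the plan says.** SAP Section 4 introduces Table 3 as the analyses meant to show the benefit of trilaciclib. The table has 17 rows, of three kinds:

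- **Eight binary endpoints** (febrile neutropenia, RBC and platelet transfusion, G-CSF, ESA, IV antibiotics, infection SAEs, pulmonary infection SAEs). SAP 6.2.7.1 gives each an ECOG-stratified difference in proportions, an 80% CI and an exact stratified CMH p-value.
- **Three duration or time-to-event endpoints** (Grade 4 neutropenia, Grade 3/4 neutropenia, first MAHE). The same section gives each a stratified p-value and a Cox hazard ratio with an 80% CI.
- **Six averages of blood counts**, derived in SAP 5.1.1.10. For these, "in addition to descriptive statistics summary, appropriate graphical display will be provided to help viewing the trend of change over time". The ANC summaries are also repeated in subsets with and without concurrent G-CSF.

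Protocol 13.4.2.1 planned more. For Part 2 it set out ANCOVA by visit on change from baseline, and by cycle on measures that include nadir and the predose value from Cycle 2 onward: "The models will include terms for treatment, ECOG at entry (0 and 1 or 2), and baseline hematologic parameter value". LS mean differences with 95% CIs were to be reported. SAP Section 7 lists among the removed items: "Analysis of covariance (ANOVA) models on hematologic parameter kinetic endpoints". It gives no reason and no replacement. (Section 7 uses the numbering of an earlier protocol amendment, 13.3.2.1, for the same heading.)

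Two other places bear on the point. SAP 6.2.7 limits between-arm comparisons to the Section 5.1.1 endpoints, where applicable, with model-based estimates where appropriate. SAP 5.2.3 and 6.2.8.2 tabulate hematology change from baseline by visit, descriptively, as safety data.

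**The concern.** The SAP's rationale is that trilaciclib protects several blood lineages and that the effect may be clearer after repeated cycles. The six averages measure the counts themselves, lineage by lineage and cycle by cycle. Yet they are the only Table 3 rows without a named estimate of the difference between arms.

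At stake are the status and the precision of whatever contrast is eventually quoted. If no method is fixed, a reader will compare plotted means by eye, or someone will choose an estimator after unblinding, although SAP Section 1 says decisions on the final analyses precede database lock. A simple difference in means also gives up precision that the protocol's model would have provided from baseline values already collected.

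**Working it through.** **Count.** 8 binary + 3 duration or time-to-event + 6 averages = 17. A between-arm estimate is specified for 8 + 3 = 11; none is specified for 6.

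**The plan's own precision figure.** Protocol 13.1 and SAP 2.3 give a 95% half-width of 0.344 SD for one arm's mean with 35 patients. Check: t(0.975, 34 df)/sqrt(35) = 2.032/5.916 = 0.3435. Reproduced. The documents give no corresponding figure for a difference between arms, and no SD or power for these endpoints.

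**Inputs for the difference.** n = 35 per arm (70 randomized 1:1). The correlation rho between the baseline and on-treatment value is not in the documents; I take 0.3 to 0.6 as the working range and also show 0.7. Results are in SD units of the count (or of its log).

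**Chance baseline imbalance.** SE = sqrt(2/35) = 0.239 SD. The probability of an absolute imbalance above 0.25 SD is 2 x [1 - Phi(0.25/0.239)] = 0.30; above 0.5 SD it is 0.036.

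**How far imbalance carries over.** A baseline difference d shifts the expected raw mean difference by rho x d. It shifts a change-from-baseline difference by (rho - 1) x d, assuming equal SDs at the two times.

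**Precision.** Unadjusted 80% half-width: t(0.90, 68 df) x sqrt(2/35) = 1.294 x 0.239 = 0.309 SD. Adjusted: t(0.90, 66 df) x sqrt(2/35) x sqrt(1 - rho^2). The equivalent unadjusted sample size is 35/(1 - rho^2).

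| Assumed rho | Variance cut (rho^2) | 80% half-width, adjusted (unadjusted 0.309) | Equivalent n per arm | Shift in raw difference if d = 0.25 SD | Shift in change score if d = 0.25 SD |
|---|---|---|---|---|---|
| 0.3 | 9% | 0.295 | 38 | 0.075 | -0.175 |
| 0.5 | 25% | 0.268 | 47 | 0.125 | -0.125 |
| 0.6 | 36% | 0.248 | 55 | 0.150 | -0.100 |
| 0.7 | 49% | 0.221 | 69 | 0.175 | -0.075 |

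The last column shows why the descriptive change-from-baseline tables do not stand in for the deleted model: unadjusted change scores carry the imbalance with the opposite sign.

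These figures use the full 35 per arm. In later cycles, with fewer patients contributing, all half-widths are wider.

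**The case against.** The strongest defence is that this is a disclosed choice in a study the protocol calls descriptive, with a sample size set on clinical grounds. Section 7 lists the removal openly, and the 11 other analyses do have estimates, including neutropenia duration and transfusion endpoints that use hemoglobin and platelet thresholds. Disclosure stands. The descriptive label does not settle the matter: the same protocol planned LS mean differences with CIs for these counts, and the SAP tests the other 11 rows at a two-sided 20% level.

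Other objections are sound and limit the point. A reader might infer any of the following, and the documents do not support them:

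- **That no difference or interval can be given.** SAP 6.2.7 leaves room for one where applicable, and the descriptive tables report n, mean and SD by arm. What is missing is a prespecified method.
- **That the unadjusted comparison is biased.** Randomization keeps it unbiased, and chance imbalance is already part of its SE. Only a fraction rho of any imbalance reaches the raw difference.
- **That baseline is ignored throughout.** Change from baseline is tabulated, but descriptively, in the safety section.
- **That the protocol already had a repeated-measures model for these six.** That model, in Protocol 13.4.2.1, covers AUC measures only. The relevant deleted model is the ANCOVA by visit and cycle.
- **That the deletion causes the late-cycle attrition problem.** ANCOVA by visit would also use only patients with data at that visit.

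At rho = 0.3 the gain is small, equivalent to about 3 extra patients per arm (38 against 35).

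**Conclusion.** The concern holds as a gap in specification with a loss of precision. Six of 17 prospectively defined analyses have no Part 2 treatment estimate named, and the protocol's baseline- and ECOG-adjusted ANCOVA was removed without replacement. The count and the removal rest on the text alone.

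The size of the loss rests on the assumed correlation: a 9% to 36% variance reduction for rho of 0.3 to 0.6, or an 80% half-width of 0.295 to 0.248 SD against 0.309 SD unadjusted, at 35 per arm. It would be wrong to go further and call the planned summaries biased or a contrast impossible. The change should be made because it is cheap and fixes the estimator before unblinding.

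**What to change.** Before unblinding, add to SAP 6.2.7.1, for each of the six averages in Section 5.1.1.10, a Part 2 model in the full analysis set adjusted for study baseline value and the randomization stratum (ECOG 0-1 vs 2). Either of two forms would do:

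- the protocol's ANCOVA by visit or cycle; or
- a repeated-measures model with treatment, cycle or visit, treatment-by-cycle, baseline and ECOG, using the log scale for ANC, platelets and lymphocytes. This extends the protocol's AUC-only model and should be described as an extension. It reduces attrition bias only if data are missing at random.

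Report the LS mean difference with the SAP's 80% CI. For ANC, make all patients regardless of G-CSF the main contrast, and keep the G-CSF subsets descriptive, since G-CSF use arises after randomization. This main contrast then includes any effect of G-CSF on the counts, and the SAP should say so. Label the results as estimation without multiplicity control. Keep the plots. Reword SAP 6.2.7 so that it agrees with 6.2.7.1 on whether these endpoints are compared, and amend Section 7 to match.

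The cost is modest programming, since baseline values are already collected and defined, and more intervals to report. With six cycles plus an overall estimate, for example, there would be 6 x 7 = 42.
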